8 STUDY TREATMENTS

8.1 INVESTIGATIONAL MEDICINAL PRODUCT(S)

SAR566658 is the only IMP in this study.

Table 1 - SAR566658 product characteristics

Items	Specification
Route of administration (ie, IV - infusion or bolus, SC, other)	IV
Dosage form (ie, solution, concentrate for solution for infusion, lyophilizate, suspension, emulsion, other)	Concentrate for solution for infusion
Concentration (mg/mL)	5
Dose/vial (mg)	125 mg/25 mL
Single or multi-dose use	Single use
Primary packaging (ie, vial, syringe, other)	Vial
Container definition	30 mL USP type I clear glass vials
Closure definition	ETFE (copolymer of ethylene and tetrafluoroethylene)-coated stoppers and seals with flip-off cap
Device (yes/no), description if any	No
Storage conditions	+ 2°C-8°C; protect from light

Abbreviations: IV: intravenous; SC: subcutaneous; USP: United States Pharmacopeia.

8.1.1 Pharmaceutical form

SAR566658 is supplied as a colorless to slightly yellow, 25 mL, extractable concentrate for solution for infusion of 125 mg in a 30 mL Type I glass vial.

8.1.2 Dilution and infusion method

Details for infusion rate and dilution/dose preparation depending on the patient dose and BSA are provided in the Pharmacy Manual.

8.1.3 Stability under light

In the conditions tested during the in-use stability study (infusion to patients at the latest 16 hours after infusion bag is prepared), SAR566658 was stable under light exposure at room temperature.

8.1.4 Compatible material for administration

The SAR566658 concentrate for solution for infusion has been shown to be compatible with prefilled infusion bags made of polyolefine or polyvinyl chloride (PVC; with di-(2-ethylhexyl) phthalate [DEHP]) and any peristaltic infusion pump that uses infusion tubing made of polyethylene or PVC DEHP-free, and an in-line filter of polyethersulfone.

Before allowing the use of any other plastic material for infusion bags and/or tubing, compatibility must be ensured.

8.2 DOSAGE AND SCHEDULE

Administration of IMP must be initiated no later than 3 days after randomization.

SAR566658 will be administered by IV infusion at a rate of 2.5 mg/min for 30 minutes and then increased to a maximal rate of 5 mg/min, in the absence of hypersensitivity reactions.

The exact dose and time of IMP administration (day/month/year, hour:minute) will be documented in the electronic case report form (eCRF).

There is no limitation in the number of cycles to be administered in the absence of major toxicity, disease progression, or any other discontinuation criteria as defined in [Section 10.3.2](#).

The patient's BSA will be calculated using their height and actual body weight to allow calculation of the dose. For patients with a BSA $>2.0 \text{ m}^2$, the dose will be calculated on the basis of 2.0 m^2 BSA.

The preferred Dubois and Dubois equation is: $\text{BSA in units of m}^2 = (\text{weight in kg})^{0.425} \times (\text{height in cm})^{0.725} \times 0.007184$.

Dose adjustment will be permitted for subsequent treatment cycles based on individual patient tolerance (see [Section 8.2.3](#)). Treatment will continue unless any of the withdrawal criteria are met, as described in [Section 10.3.2](#).

8.2.1 Dose of IMP per administration

Part 1 (overexpressing CA6)

Patients will be randomly allocated to receive 1 of the following 2 doses in a 1:1 ratio:

- Cohort 1: 90 mg/m^2 of SAR566658 on D1 and D8 repeated every 21 days. This will constitute 1 cycle of treatment.
- Cohort 2: 120 mg/m^2 of SAR566658 on D1 and D8 repeated every 21 days. This will constitute 1 cycle of treatment.

Part 2 (expansion/overexpressing CA6 and mild CA6 expression cohorts)

SAR566658 will be administered at the dose of 90 or 120 mg/m^2 on D1 and D8 repeated every 21 days, depending on the dose selected from Part 1.

8.2.2 Premedication

Premedication with histamine H1 antagonist (diphenhydramine 50 mg or equivalent given orally approximately 1 hour before SAR566658 administration) is required for all patients.

Ocular prophylaxis

Eye drops (ie, topical artificial tears and/or hyaluronic ophthalmic gel) are strongly recommended to be instilled in each eye up to 6 times a day during the study treatment period in all patients. These eye drops should not be applied within 15 minutes (before or after) of preventive corneal toxicity drop instillation.

The potential ocular/visual toxicity could include, but is not limited to, blurred vision, dry eye, and photophobia. Curative treatment may be used as recommended by an ophthalmologist.

All patients in Part 1 and Part 2 of this study will receive corneal toxicity (keratopathy/keratitis) prophylaxis around the time of each infusion, to include:

- Vasoconstrictor (phenylephrine 2.5% ophthalmic solution or equivalent) will be administered to each eye with 1 drop prior to the start of infusion and then 1 drop every 20 minutes, with a total of 3 drops.
- Corticosteroid ophthalmic solution, ointment, or gel (such as dexamethasone 0.16% or equivalent) administered to each eye 3 times a day (morning, midday, and night), starting on the day of the infusion and for 2 days after infusion, for a total of 3 days of steroid ophthalmic therapy including Day 1 of each cycle.
- Use of cold eye mask/pad (unless patient cannot tolerate it), from start until end of infusion.

Before implementation of the preventive measures, it should be ensured that the patient has no contraindication as per labeling of the topical treatment used. Patients should be informed that they will experience blurred vision that may last up to 1 to 2 hours after application of the ocular preparations.

8.2.3 Dose modification and dose delay

Dose modification (reduction or omission) or cycle delay is planned in case of AEs. Dose modification will be made according to the worst grade toxicity observed within a cycle. Adverse events will be graded according to NCI CTCAE v4.03.

Dose may be reduced depending on the severity of the AE.

If a patient experiences several AEs and there are conflicting recommendations, the most conservative recommended dose adjustment (dose reduction/omission/delay appropriate to the most severe AE) should be followed.

8.2.3.1 Dose modification

Dose can be reduced for SAR566658 when necessary, as described in the following sections. The dose, which has been reduced due to an AE, must not be re-escalated. Up to a maximum of 2 dose

reductions will be allowed per patient. If a third dose reduction is required per the modifications below, the patient should discontinue study treatment. Dose levels for each arm in case of dose reduction are described in [Table 2](#) below.

The patient may have the Day 8 dose omitted if an AE occurs and they have not recovered on the theoretical day of infusion. The patient will receive the next cycle after recovery from the AE, as described.

Table 2 - Dose reduction levels

	Initial dose (mg/m ²)		Dose reduction 1 (mg/m ²)		Dose reduction 2 (mg/m ²)
SAR566658	90	→	75	→	60
SAR566658	120	→	90	→	75

8.2.3.2 Treatment delay

At Day 22, a treatment delay ≥ 4 days should be justified (ie, to be reported in the eCRF). Study treatment may be delayed up to 2 weeks to allow recovery from acute toxicity. In case of a delay due to IMP-related AEs ≥ 2 weeks (except for alopecia), the patient will be withdrawn from the treatment.

The dose of SAR566658 will be modified in case of AEs. Dose modifications are summarized in [Table 3](#).

Table 3 - Dose modifications for SAR566658

Adverse event	Grade 2	Grade 3	Grade 4
Diarrhea	Delay ^a next infusion until recovery (Grade ≤1). No dose reduction required.	On Day 8, omit the dose. On Day 22, delay ^a next infusion until recovery (Grade ≤1): - 1st episode: reduce dose by 1 dose level, - 2nd episode: reduce dose by 1 more dose level, - 3rd episode: withdraw from study treatment.	
Creatinine increase	No delay, in case of creatinine >1.5 x ULN to calculate creatinine clearance (CLCr) ^b on D21: - If ≥50 mL/min, no dose modification, - If clearance ≥30 mL/min and < 50 mL/min, reduce dose by 1 dose level, - If clearance <30 mL/min, withdraw from study treatment.		
Peripheral neuropathy	No delay. Reduce by 1 dose level.	Delay ^a next infusion until recovery (Grade ≤1): - 1st episode: reduce dose by 1 dose level, - 2nd episode: reduce dose by 1 more dose level, - 3rd episode: withdraw from study treatment.	Withdraw from study treatment.
Total bilirubin elevation	In case of bilirubin >1.5 x ULN: On Day 8, omit the dose. On Day 22, delay ^a until recovery to bilirubin ≤1.5 x ULN and then reduce by 1 dose level. If no recovery after 2 dose reductions, withdraw from study treatment.		
Transaminases elevation	On Day 8, omit the dose. On Day 22, delay ^a until recovery to AST/ALT Grade ≤1. No dose adjustment.	On Day 8, omit the dose. On Day 22, delay ^a until recovery to AST/ALT Grade ≤1: - 1st episode: reduce dose by 1 dose level, - 2nd episode: reduce dose by 1 more dose level, - 3rd episode: withdraw from study treatment.	Withdraw from study treatment.

Dose reduction levels provided in [Table 2](#).

^a A maximum of 2 weeks delay at D22, otherwise the patient will be withdrawn from study treatment.

^b As per Cockcroft-Gault formula; see [Appendix E](#).

Abbreviations: ALT: Alanine aminotransferase; AST: Aspartate aminotransferase; D: day; ULN: upper limit of normal.

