--	--

	
E 06. Adverse events (AEs) (excluding alopecia and those listed in the specific exclusion criteria) from any prior anticancer therapy of Grade >1 (National Cancer Institute Common Terminology Criteria for Adverse Events [NCI CTCAE] v4.03; see Appendix D) at the time of randomization.
 
E 07. Wash out period of less than 3 weeks or 5 half-lives from previous antitumor chemotherapy, immunotherapy, or any investigational treatment.
 
E 08. Patient has received wide field radiotherapy ≤ 4 weeks prior to starting study treatment, or limited field radiation for palliation ≤ 2 weeks prior to starting study treatment, or has not recovered from the side effects of such therapy.
 
E 09. Patient has undergone major surgery ≤ 3 weeks prior to starting study treatment, or has not recovered from the side effects of major surgery.
 
E 10. History of brain metastasis (other than totally resected or previously irradiated and nonprogressive/relapsed), spinal cord compression or carcinomatous meningitis, or new evidence of brain leptomeningeal disease.
 
E 11. Prior malignancy. Adequately treated basal cell or squamous cell skin or superficial (pTis, pTa, and pT1) and bladder cancer are allowed, as well as any other cancer for which treatment has been completed ≥ 3 years ago and from which the patient has been disease-free for ≥ 3 years.
 
E 12. Participation in another clinical trial and any concurrent treatment with any investigational drug within 30 days prior to randomization.
 
E 13. Prior treatment with eribulin as last therapy prior to enrollment, or prior maytansinoid treatments (DM1 or DM4 antibody-drug conjugates [ADCs]).
 
Related to study treatment
 
E 14. Acquired immunodeficiency syndrome (AIDS-related illnesses) or known HIV disease requiring antiretroviral treatment.
 
E 15. Known active hepatitis A, B, or C infection that requires treatment.
 
E 16. Known intolerance to infused protein products including other monoclonal antibodies and ADCs.
 
E 17. Poor bone marrow reserve as defined by absolute neutrophil count $< 1.5 \times 10^9/L$ or platelets $< 100 \times 10^9/L$ or hemoglobin < 9 g/dL.
 
E 18. Poor organ function as defined by 1 of the following:
 
a) Total bilirubin > 1.5 x upper limit of normal (ULN) (except patients with Gilbert's syndrome: total bilirubin ≤ 3.0 x ULN, with direct bilirubin ≤ 1.5 x ULN),b) Aspartate aminotransferase, alanine aminotransferase, or alkaline phosphatase > 2.5 x ULN; except > 5 x ULN in case of documented liver metastasis or alkaline phosphatase > 5 x ULN in case of documented bone metastasis,c) Serum creatinine > 1.5 x ULN, except if calculated creatinine clearance ≥ 60 mL/min (as per Cockcroft-Gault formula, see Appendix E). 
E 19. Symptomatic peripheral neuropathy Grade ≥ 2 (NCI CTCAE v4.03).

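### Table 3's bilirubin limits leave out the Gilbert's exception in E 18 a), so a patient back at her accepted entry value cannot be re-dosed; the transaminase row has the same gap if Grade 1 ends below 5 x ULN

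*Protocol*

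**What the plan says.** **Entry.** E 18 (Protocol Synopsis and Section 7.2.2) excludes poor organ function. Part a) sets the general bilirubin exclusion at "Total bilirubin > 1.5 x upper limit of normal (ULN"), with an exception for Gilbert's "syndrome: total bilirubin ≤ 3.0 x ULN, with direct bilirubin ≤ 1.5 x ULN". Part b) excludes AST or ALT above 2.5 x ULN, "except > 5 x ULN in case of documented liver metastasis".

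**Re-dosing.** In Table 3 the bilirubin row applies above 1.5 x ULN. Day 8 is omitted, and Day 22 is delayed "until recovery to bilirubin ≤1.5 x ULN and then reduce by 1 dose level". For Grade 2 transaminase elevation, Day 8 is omitted and Day 22 is delayed "until recovery to AST/ALT Grade ≤1. No dose adjustment". The Grade 3 entry has the same recovery target and adds dose reductions; Grade 4 means withdrawal. Neither row mentions Gilbert's syndrome, liver metastasis or baseline.

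**Time limit.** Footnote a, attached to the delay in both rows, reads "A maximum of 2 weeks delay at D22, otherwise the patient will be withdrawn from study treatment". The body text of Section 8.2.3.2 also withdraws patients at 2 weeks, but only when the delay is due to events related to the study drug. Section 8.2.3.1 says of an omitted Day 8 dose: "The patient will receive the next cycle after recovery from the AE, as described".

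**The concern.** Table 3's bilirubin limit is the same number as the general entry limit in E 18 a). The row appears to carry over the general rule without its exception. Some admitted patients then start treatment at a value that can never count as recovered. If such a patient has an on-treatment rise that fully resolves to her entry value, the table still bars the next dose, and footnote a takes her off treatment permanently.

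The stake is mainly at patient level: loss of treatment at a liver value the protocol accepted. She also remains in the all-treated population, on which the primary ORR analysis is done (Sections 11.3.1 and 11.4.4.1).

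**Working it through.** No sample size or error rate is in question. The check compares entry ceilings with re-dosing ceilings on the ULN scale.

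**1. Bilirubin (documents alone)**
- General entry ceiling (E 18 a): 1.5 x ULN. Re-dosing ceiling (Table 3): 1.5 x ULN. Gap: 1.5 − 1.5 = 0, so most patients face no conflict.
- Gilbert's entry ceiling: 3.0 x ULN. Re-dosing ceiling: 1.5 x ULN. Gap: 3.0 − 1.5 = 1.5 x ULN.
- Affected baselines: above 1.5 and up to 3.0 x ULN.
- Example: entry 2.5, on-treatment rise to 3.5, return to 2.5. She is back at baseline, but 2.5 > 1.5, so she has not recovered under Table 3.

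**2. Transaminases (one assumption)**

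The protocol grades by NCI CTCAE v4.03 but does not print the Grade 1 ceiling, U. With the liver-metastasis entry ceiling of 5 x ULN:

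| Assumed U (x ULN) | Affected baselines (x ULN) | Gap (x ULN) |
|---|---|---|
| 2.5 | >2.5 to 5 | 5 − 2.5 = 2.5 |
| 3 (working assumption) | >3 to 5 | 5 − 3 = 2 |
| 4 | >4 to 5 | 5 − 4 = 1 |
| 5 or more | none | none |

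**3. Does other text cure the gap?**
- Flow chart footnote h (Section 1.3) refers to recovery to baseline after Grade 3 or worse liver tests, but it sets how long extra tests continue, not when to re-dose.
- Section 8.2.3.3.3 gives the investigator discretion only for toxicities not covered elsewhere.
- Neither supplies the missing exception.

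**4. Timing for a Cycle 1 event**
- Latest re-dosing date: Day 22 + 14 = Day 36.
- First 6-weekly scan: Day 1 + 42 = Day 43, which is 43 − 36 = 7 days later.
- End-of-treatment tumor assessment (Section 10.1.5), 25 to 35 days after the last infusion: Day 26 to 36 if only Day 1 was given, or Day 33 to 43 if Day 8 was also given.
- Section 9.1.2 continues scans after discontinuation until progression or study cut-off.

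**The case against.** **Withdrawal is not unambiguous.** The body text ties the 2-week rule to drug-related events, and a patient back at her entry value arguably has none ongoing. The bilirubin row also ends by withdrawing patients who have not recovered after two dose reductions, which sits awkwardly with withdrawal at the first non-recovery. This stands as a reason not to call withdrawal certain. It does not remove the problem: footnote a has no such limit, and the row bars re-dosing in either case.

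**A stricter limit after an on-treatment liver event may be deliberate.** It would be a cautious choice, and hepatic safety data in the Investigator's Brochure are not available here. No rationale is given, though Table 3 gives none for any row. The match with the general entry limit suggests an omission but does not prove one.

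**Stronger readings that the documents do not support**
- *A Gilbert's patient stable at 2 x ULN loses Day 8 from the start.* The trigger read literally says so. But Section 8.2.3 opens with "Dose modification (reduction or omission) or cycle delay is planned in case of AEs", and Section 8.2.3.2 describes delay as time to recover from acute toxicity. An unchanged baseline value is not clearly either.
- *An affected patient is withdrawn before any scan and cannot be a responder.* The end-of-treatment assessment and continued scans mean a confirmed response is not ruled out.
- *The gap reduces power or biases dose selection.* The documents give no count of affected patients. Section 4.1.2 describes liver abnormalities in the first-in-human study as low grade. Section 4.2 mentions a responding TNBC patient with liver metastasis but gives no liver values for her.

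**Conclusion.** The bilirubin inconsistency holds from the protocol text alone. Patients admitted under the Gilbert's exception with total bilirubin above 1.5 and up to 3.0 x ULN cannot meet the re-dosing limit by returning to baseline, and footnote a then withdraws them after 2 weeks. Footnote a and the body text disagree on whether the event must be drug-related.

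The transaminase inconsistency is conditional: it holds for any Grade 1 ceiling below 5 x ULN, and on the assumed 3 x ULN it covers baselines above 3 and up to 5 x ULN.

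Only a patient with a raised admitted baseline who worsens and then returns to baseline but no lower is affected. Few are likely, and no effect on power or dose selection is shown. Severity: minor; a cheap improvement to the dosing rules.

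**What to change.** 1. **Bilirubin row, patients enrolled under the Gilbert's exception.** Replace 1.5 x ULN by E 18 a)'s own limits in both places. Act if total bilirubin exceeds 3.0 x ULN or direct bilirubin exceeds 1.5 x ULN. Recovery is total at most 3.0 x ULN and direct at most 1.5 x ULN. In the example, 2.5 x ULN then counts as recovered if direct bilirubin is within its limit. Fixed limits are better here than a baseline target: under a baseline rule, a drift from 2.0 to 2.1 x ULN would still force a dose reduction, which Section 8.2.3.1 does not allow to be reversed.
2. **Transaminase row, patients enrolled under the liver-metastasis exception.** Set recovery to Grade 1 or below, or baseline, with baseline as defined in Section 11.4. State that a value at or below baseline triggers no omission or delay.
3. **Footnote a and body text.** Run the 2 weeks to these targets, and state once whether withdrawal requires a drug-related event.
4. **Keep** the existing dose-reduction steps and the Grade 4 withdrawal. Leave the combination of ALT above 3 x ULN and total bilirubin above 2 x ULN as the seriousness criterion it is in Section 10.4.1.2. As a dosing bar it would block, for example, a Gilbert's patient with liver metastasis admitted at ALT 4 and bilirubin 2.5 x ULN.

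**Cost.** A short amendment with the usual ethics approval. Conjugated bilirubin is already in the chemistry panel, so no new data are needed, and the SAP does not change. The downside is that a few patients would be re-dosed at higher liver values after an on-treatment event, within the limits accepted at entry.

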8.2.3.3 Specific recommendations

8.2.3.3.1 Hypersensitivity reactions

Premedication with histamine H1 antagonist (diphenhydramine 50 mg given orally approximately 1 hour before SAR566658 administration) is required for all patients.

Infusion-related hypersensitivity reactions (NCI CTCAE v4.03 term ‘allergic reaction/cytokine release syndrome/anaphylaxis’ [[Appendix D](#)]) are defined as events occurring on the day of IMP infusion.

Management plans for infusion-related hypersensitivity reactions are described in [Table 4](#).

Table 4 - Infusion-related hypersensitivity reactions and recommendations

Symptom severity (NCI CTCAE v4.03)	Intervention recommendation
Mild Grade 1 (eg, localized cutaneous reaction, pruritus, flushing, rash)	Continue SAR566658 infusion Give diphenhydramine 50 mg IV (or equivalent) and/or dexamethasone 10 mg IV
Moderate eg, Grade ≤ 2 nausea, headache, tachycardia, hypotension, rash, shortness of breath	Stop SAR566658 infusion Give diphenhydramine 50 mg IV (or equivalent) and/or dexamethasone 10 mg IV SAR566658 may be resumed ^a only after patient recovery (all signs and/or symptoms of infusion-related reaction disappear or return to Grade ≥ 1); infusion should be resumed, at half the previous infusion rate
Severe and life-threatening eg, Grade ≥ 3 symptomatic bronchospasm, urticaria lesions covering >30% BSA, hypotension, angioedema	Stop SAR566658 infusion Give diphenhydramine 50 mg IV (or equivalent) and/or dexamethasone 10 mg IV and/or epinephrine as needed Definitive treatment discontinuation

^a SAR566658 is stable for a maximum of 16 hours in the infusion bag at room temperature. If necessary, a new infusion should be prepared with the remaining dose to be administered.

Abbreviations: BSA: body surface area; IV: intravenously; NCI CTCAE: National Cancer Institute Common Terminology Criteria for Adverse Events.

8.2.3.3.2 Corneal toxicity

The potential corneal toxicity could include, but is not limited to, blurred vision, dry eye, and photophobia. Treatment with topical steroids or other medications (such as hyaluronic acid gel) may be used as recommended by an ophthalmologist. Recent findings from ocular examinations performed to assess and follow-up patients experiencing corneal toxicity (commonly reported as “keratitis”) from other DM4 immuno-conjugate drugs indicate that the primary corneal lesion induced is rather reversible, centripetal (moving from periphery towards the center upon resolution) corneal microcysts and/or deposits, and is noninflammatory in nature (5). Similar findings were observed in the SAR566658 FIH study (TED10499). Therefore, it is thought that corneal toxicity would be better described by distinguishing between keratitis and keratopathy.

Keratitis would not be limited to corneal inflammation but can be keratopathy as well. Corneal toxicity management will be applicable to both keratitis and keratopathy. The current CTCAE v4.03 is not fully adapted to eye toxicity reporting and does not include a grading tailored to keratopathy nor to asymptomatic corneal findings. The grading currently applied to keratitis is extended to keratopathy with the option to use G1 as severity grading (eg, asymptomatic corneal findings only observed on ocular examinations) to properly document corneal findings evolution up to complete recovery.

Corneal toxicity management

In case of occurrence of a corneal toxicity, the management of the keratopathy/keratitis is described below in [Table 5](#).

Table 5 - Corneal toxicity (keratopathy/keratitis) management recommendation

Symptom severity (NCI CTCAE v4.03) ^a	Intervention recommendation

Asymptomatic keratitis (Grade 1)^a
 
Corneal lesions only observed on routine ocular examination and not requiring topical treatment
	
 • Next infusion at the same dose, with or without dose delay, depending on the recommendation from the ophthalmologist (nature and extent of the lesion). • Perform the complete ocular examination, including assessment of ocular/visual symptoms, visual acuity, full ocular tests including slit lamp with fluorescein under dilatation, and Schirmer's test preferably with anesthetics, and then repeat every cycle.

Grade 2 keratitis^b
 
Symptomatic or requiring topical treatment (curative) or limiting instrumental activity of daily life
	
 • Perform the complete ocular examination, including assessment of ocular/visual symptoms, visual acuity, full ocular tests including slit lamp with fluorescein under dilatation, and Schirmer's test preferably with anesthetics. Repeat the complete ocular examination on a weekly basis until resolution (asymptomatic), and then every cycle. • Start curative treatment per ophthalmologist recommendation (eg, topical steroids). • Dose delay until resolution (asymptomatic). • Continue ocular primary prophylaxis before infusion and dose reduction at the next cycle^c • Management of study drug upon recurrence to be discussed according to grade of the event at recurrence, clinical benefit from study drug, and recommendation from the ophthalmologist.

Grade 3 keratitis^b
 
Decline in vision (worse than 20/40 but better than 20/200) or limiting self-care activity of daily life
	
 • Perform the complete ocular examination, including assessment of ocular/visual symptoms, visual acuity, full ocular tests including slit lamp with fluorescein under dilatation, and Schirmer's test preferably with anesthetics. Repeat the complete ocular examination on a weekly basis until resolution (asymptomatic), and then every cycle. • Start curative treatment per ophthalmologist recommendation (eg, topical steroids). • Dose delay until resolution (asymptomatic). • Continue ocular primary prophylaxis before infusion and dose reduction at the next cycle^c • Permanently discontinue SAR566658 upon recurrence.

Grade 4 keratitis
 
Perforation or blindness (20/200 or worse)
	
 • Complete ocular examination on a weekly basis until resolution (asymptomatic)^b. • Start curative treatment per ophthalmologist recommendation. • Permanently discontinue SAR566658.

a Grading of keratitis starts at Grade 2 in NCI CTCAE v4.03. The option is to use Grade 1 as severity grading (eg, asymptomatic corneal findings only observed on ocular examinations) to properly document corneal findings evolution up to complete recovery. The same NCI CTCAE v4.03 grading is applied to keratopathy.

b When possible at the site, photographs should be taken when findings are first documented and to follow progression when relevant. Any additional relevant ocular examination can be done if indicated.

c Measure intraocular pressure by tonometry whenever clinically indicated and at end of treatment.

